6.2. Missing Data

Information about the proportion with missing information will be provided, informing about the variations of the "n" (sample size), investigating and describing the reasons that generated the omission.

Variables with more than 10% of data missing are not suitable for techniques for imputation of values, and retention of the subject or variable in the study will be questioned and decided by the steering committee. Imputation of missing data can be considered after analysis of the type of mechanism that led to it.

RCT should preferably analyze all participants by intention to treat (ITT), so that all of those randomized and allocated to a group should be analyzed at the end of the study, irrespective of diversions from the therapeutic protocol or of dropouts. We will use Last Observation Carried Forward (LOCF), a single

imputation technique that imputes the last measured outcome value for participants who either drop out of a clinical trial or for whom the final outcome measurement is missing. LOCF is usually used in the longitudinal study design where the outcome is measured repeatedly at pre-specified intervals. LOCF usually requires there is at least one post-baseline measure.

We will perform imputation of missing entries from incomplete data sets m times; the imputed values are drawn from a distribution. The random draw simulation does not include the uncertainty in the model parameters. A better approach is to use Markov Chain Monte Carlo (MCMC) simulation. This step results in complete data sets. We will analyze each of the complete data sets and finally integrate the results of the m analysis into a final result. For data imputation on categorical variables, the missing values will be treated as a separate category by themselves. We can create another category for the missing values and use it as a different level. After this procedure we will use multiple imputation.

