Data will be reported quantitatively. All analyses will be performed from the intention-to-treat principle. Missing data on background variables will be dealt with by multiple imputation. Final data analysis will begin when the last participant in the multicentric RCT has completed the follow-up period. The primary endpoint, work absenteeism due to illness, will be reported as the total number of sick days with standard deviation. Total days of absenteeism will be analysed using a Bayesian negative binomial regression with a fixed effect for BCG, hospital, professional category, age, enrolment week and number of average workdays per week. The brm function from the R package "brms" will be used for fitting the negative binomial model. The effect will be reported as a relative risk with 95% confidence interval (CI). Please refer to section interim analysis for type-1 error control and power.

Similar regression models will be used for secondary endpoints. Cumulative incidence outcomes will primarily be analysed using Cox Proportional Hazard Regression.

Continuous baseline characteristics will be reported as means with the standard deviation or medians with the inter-quartile range, as appropriate. Categorical baseline characteristics will be reported as count and percentage. No statistical testing for baseline characteristics will be reported.

Please refer to the Data Analysis Plan for more details.

Interim analysis

Every month, an interim analysis will be conducted for each study site and of the combined dataset. Interim analyses will start after the 200th participant has been recruited across the two sites. The primary endpoint will be analysed as described above. The Bayesian model yields a posterior distribution of the relative risk (RR). The posterior probability of the superiority hypothesis ($RR < 1$) will be calculated. If during any of the interim analyses, the posterior probability of superiority is > 0.995 , a conclusion is reached, and the trial will be stopped.

Monthly, the following secondary endpoints will be reported from the sites: hospital admissions, and deaths.

IMPLEMENTATION

Inception

The study will begin with an inception meeting to be held in Cape Verde or virtually, depending on travel and quarantine recommendations at the time. Besides administrative issues, the meeting will address:

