Data will be reported quantitatively. All analyses will be performed from the intention-to-treat principle. Missing data on background variables will be dealt with by multiple imputation. Final data analysis will begin when the last participant in the multicentric RCT has completed the follow-up period. The primary endpoint, work absenteeism due to illness, will be reported as the total number of sick days with standard deviation. Continuous baseline characteristics will be reported as means with the standard deviation or medians with the inter-quartile range, as appropriate. Categorical baseline characteristics will be reported as count and percentage. Statistical testing for baseline characteristics will be performed. Days of absenteeism will be analysed using a Bayesian negative binomial regression with a fixed effect for BCG, hospital, professional category, age, enrolment week and number of average workdays per week. Incidence data will be analysed in Cox proportional hazards models. Monthly, data on absenteeism by randomization group will be reported to the DSMB.

Trial registration

The trial is registered at clinicaltrials.gov. (<https://clinicaltrials.gov/ct2/show/NCT04641858>)

Funding

EDCTP is funding the run-in costs for the BCG-COVID-RCT, including trials in the respective countries and for training and management.

Study management, monitoring and quality control

The project is led by an International Steering Committee (ISC) consisting of PIs in each of the five countries involved: [name] (international coordinator), PI from Denmark; [name], PI from Guinea-Bissau; [name], PI from Portugal; [name], PI from Cape Verde; and [name], PI from Mozambique. The overall coordination is the responsibility of the Danish partner. The leader has extensive leadership experience from running a Center of Excellence in Denmark and the research group of the Bandim Health Project in Bissau for many years. The Bandim Health Project has a history of past collaboration with the Portuguese partner. The research group will hold teleconferences at least once a week with a formal pre-established agenda on training, enrollment, follow-up, losses to follow-up, staff turnover, vaccine logistics, quality control of data collection, data entry and database management, interim analysis, communication and dissemination activities, other risks. Decisions from each meeting are recorded by the coordinator.

2. Definitions

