6.1. General statistical methodology

The database system for both inclusion procedures and follow-up is REDCap (www.project-redcap.org), and the instruments have been developed by the Institute of Hygiene and Tropical Medicine at NOVA University.

Data entry for both inclusion and follow-up procedures is conducted online using the browser version, which means that no participant data is stored locally and that the study responsible(s) can monitor the data collection in real-time.

The randomization code was developed by the trial statistician, [name]. This code produces an allocation table for all the stratification layers and all the sites, with block sizes varying randomly between 4 and 6 within each individual stratum. The allocation table used for the study has not been seen and is not available to any of the researchers involved in the study and it was implemented by an independent statistician, [name], in Bissau.

From the databases of the trials in Guinea-Bissau and Mozambique, their analysis will be performed by either STATA version 17 software (Stata, College Station, TX) or SPSS version 26.

The combined data analysis will begin when the last participant in the multicentric RCT has completed the follow-up period or after the 182 day of the study and data has been cleaned.

Descriptive statistical techniques (absolute and relative frequency distribution) will be used to analyze the quality of the database through the evaluation of two aspects: completeness (field filling) and consistency (consistency between the categories marked in two related fields). The completeness indicator will be calculated as the proportion of filled fields in relation to the total of records, in percentage. Regarding completeness, the results will be categorized as the percentage of records without filling out as follows: excellent (<10% of records without filling out), regular (11 to 30%) and low (>30% of records without filling out).

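### SAP 6.2 rules out imputation above 10% missing and lets the steering committee decide on dropping subjects or variables, against the plan's own uncapped multiple imputation and intention to treat

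*SAP*

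**What the plan says.** The protocol (Statistical methods, Data analysis) gives a rule without a limit: "Missing data on background variables will be dealt with by multiple imputation". The SAP's statistical analysis summary repeats that sentence unchanged and adds "All analyses will be performed from the intention-to-treat principle".

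SAP 6.2 then sets a limit. "Variables with more than 10% of data missing are not suitable for techniques for imputation of values", and above that level "retention of the subject or variable in the study will be questioned and decided by the steering committee". No criteria for the decision are given. The section does not say when it is taken, or whether it is taken without knowledge of treatment arm.

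Later in the same section the SAP plans repeated imputation with pooling of the results, makes missing values of categorical variables a category of their own, and closes with "After this procedure we will use multiple imputation". The 10% limit is not mentioned again. For dropouts and missing final outcomes, SAP 6.2 has a different rule: "We will use Last Observation Carried Forward (LOCF), a single" imputation method.

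The primary model is a Bayesian negative binomial regression with a "fixed effect for BCG, hospital, professional category, age, enrolment week and number of average workdays per week".

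**The concern.** The share of values missing does not decide whether multiple imputation is valid. That depends on the missingness mechanism and on the imputation model, and SAP 6.2 itself refers to the mechanism. The cost of not imputing grows with the share missing, so a ceiling withdraws the method where it does most good. The SAP gives no reason for 10%.

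What replaces imputation above the ceiling matters more. Removing subjects means that not everyone randomised is analysed, with possible selection bias if incomplete baseline data go with poorer health or less contact. Removing the variable changes a pre-specified primary model. Either choice would be made after the extent of missing data is known, by a committee made up of the country investigators. The SAP lists participants, research assistants and analysts as blinded (2.1) and keeps the allocation table from the researchers (6.1), which gives some protection, but 6.2 does not tie the decision to blinded data.

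The SAP also foresees missingness in this range. Its completeness scale in 6.1 has bands described as "regular (11 to 30%) and low (>30% of records without filling out".

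**Working it through.** **Step 1. The rules side by side, for a background variable**

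| Share missing | Protocol, Data analysis | SAP, Statistical analysis summary | SAP 6.2, ceiling | SAP 6.2, closing part |
|---|---|---|---|---|
| 10% or less | multiple imputation | multiple imputation | imputation allowed | multiple imputation |
| More than 10% | multiple imputation | multiple imputation | not suitable; committee decides on subject or variable | multiple imputation |

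The rules agree up to 10% and conflict above it. The conflict lies between the two documents and also within the SAP. It covers background variables only, because that is all the protocol's imputation sentence covers.

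**Step 2. Which primary-model covariates are exposed**

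Professional category is a randomisation stratum, and hospital and enrolment week are fixed at enrolment, so these three should be almost complete. That leaves age and average workdays per week. Both are numeric, so the separate category for missing categorical values does not keep their incomplete cases in the model. Neither document states an expected share missing for either.

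**Step 3. The plan's own sample size**

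Inputs (Protocol and SAP, Sample size): means 5 and 4 days, SD 5, 80% power, alpha 0.05, 5% loss, 1050 randomised 1:1. The SAP (6.1) specifies two-tailed tests.

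- n per arm = 2 × 5² × (1.96 + 0.8416)² / 1² = 392.4, so 393 per arm and 786 in total.
- With 5% loss: 786 / 0.95 = 827.4, so 828.

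The stated 1050 does not follow from these inputs at 80% power. SAP section 3 explains it as three sites of 350, set against a minimum of 1000 from another group. With 1050 × 0.95 = 997.5 followed, or 498.75 per arm, power is 88%. The plan therefore has some reserve over its stated 80%.

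**Step 4. Illustration: participants lacking one covariate are dropped**

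Power = Φ(1 / (5 × √(2/n)) − 1.96), with n = 498.75 × (1 − m). The values of m are assumptions.

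| m | n per arm | 1 / (5√(2/n)) | Power |
|---|---|---|---|
| 0% | 498.75 | 3.158 | 0.8846 |
| 10% | 448.9 | 2.996 | 0.8500 |
| 20% | 399.0 | 2.825 | 0.8065 |
| 30% | 349.1 | 2.642 | 0.7525 |

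Power reaches the stated 80% when n falls to 393 per arm: 1 − 393 / 498.75 = 0.212, or about 21% dropped. If both exposed covariates were missing independently at 15%, n = 498.75 × 0.85² = 360.3 and power is 0.7657.

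**Step 5. The same threshold on a negative binomial scale**

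Mean 5 and SD 5 give size 5² / (25 − 5) = 1.25. Taking that size in both arms, n per arm = (1.96 + 0.8416)² × [(1/5 + 1/1.25) + (1/4 + 1/1.25)] / (ln 0.8)² = 323. Then 1 − 323 / 498.75 = 0.352, so about 35% could be dropped before power fell below 80%.

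**The case against.** The strongest reply has four parts.

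- **The SAP may refine the protocol.** The protocol refers to the analysis plan for detail, so a limit there need not be a contradiction. This fails, because the SAP's own summary repeats the uncapped rule and 6.2 itself returns to multiple imputation without the limit.
- **The ceiling may never be reached.** Age and workdays per week are simple baseline items, and nothing in the documents suggests that either would pass 10% missing. This stands, and it limits the practical weight of the point.
- **The committee may drop the variable and keep every participant.** This also stands. A reader might infer that the primary analysis becomes complete-case by rule. The text does not say so: it gives the committee a choice, and 6.2 restates that all randomised participants should be analysed. What remains is that the choice is open and has no criteria.
- **The stated power is robust.** A reader might infer that the 80% is lost once 10% is passed. It is not: it lasts until about 21% are dropped on the two-means calculation, and about 35% on the negative binomial one.

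A reader might also extend the ceiling to the outcome. With 182 / 14 = 13 two-weekly calls and 2% of them missed independently, 1 − 0.98¹³ = 23% of totals would lack at least one call. The documents do not support treating those totals as missing variables barred from imputation. After 18 days without an answer the protocol retrieves absence from hospital registries, workplace registers supplement the calls where they exist, and SAP 6.2 assigns missing outcomes to last observation carried forward. Whether that outcome rule is a good one is a separate question.

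**Conclusion.** The point holds for background covariates. SAP 6.2 conflicts with the protocol, with the SAP's own summary and with its own closing part for any background variable more than 10% incomplete. It also opens a data-dependent route, without criteria, to removing randomised participants or a pre-specified covariate, against intention to treat. That conclusion rests on the text alone and needs no assumption about the data.

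The size is uncertain. The fall in power from 88% to 85%, 81% and 75% assumes 10%, 20% or 30% missing on one covariate, removal of exactly those participants, and a two-means approximation in place of the planned model. It does not count selection bias, which cannot be sized from the documents. The change is worth making because it is cheap and protects the analysed population. The documents do not show that the primary analysis is bound to lose participants or its stated power.

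**What to change.** In SAP 6.2:

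- Delete the 10% ceiling and the committee decision on retaining subjects or variables.
- State that missing background covariates in the analysis models are multiply imputed whatever the percentage missing, in line with the protocol's data analysis section and the SAP's statistical analysis summary.
- State that no randomised participant is excluded because a covariate is missing.
- Report the share missing for each model covariate by arm, and add a sensitivity analysis that varies the missing-data assumption when it exceeds 10%.

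The cost is a sentence or two in SAP 6.2 and one extra sensitivity analysis, with no change to data collection or trial conduct. This change leaves the rule for missing absenteeism reports as it is; that rule needs its own review.

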The participants in this research are HCW. Prior to the initiation of the trial, the hospital director will inform the department heads about the trial. For recruitment we performed a rapid test (POC test) for antibodies against SARS-CoV2 using the COVID-19 IgG/IgM CTK OnSite COVID-19 IgG/IgM Rapid Test (<https://ctkbiotech.com/covid-19/>). The test is performed by collecting a drop of blood (maximum 0.4 ml of blood) from a fingerstick. The participant was informed about the POC test result and the interpretation of what it means to having or not having IgM and/or IgG antibodies. If the result is positive for IgM antibodies, we recommend that the HCP be tested for SARS-CoV2 with a swab in the throat (PCR test), according to the recommendations of local health authorities. The BCG vaccine was administered by people trained to administer vaccines by the intradermal technique. The injection site should be clean and dry. The vaccine was injected intradermally on the outer side of the upper arm, corresponding to the area of the distal insertion of the deltoid muscle (about one-third down the upper arm).

Follow-up will last for 6 months (182 days). Every second week, participants will be contacted over telephone and interviewed for symptoms and absenteeism from work. By the end of follow-up,

participants will be invited for another POC test for COVID-19 serology. The study relies on bi-weekly telephone follow-up. Participants have indicated whether they prefer to be contacted during the morning, the afternoon or at any time during the day. The responsible assistant conducts the telephone follow-up every day and introduces the data on absenteeism and causes, COVID-19 testing (if done) and their results on the WiFi-connected tablet during the interview. This data can be supplemented by daily workplace presence registry information (where present). An explicit permission for this procedure will be requested from the participant during informed consent procedures at enrolment.

5. Endpoint variables

The endpoint variables are described in Table 1

Table 1 – Definition of end-points variables

Variable	Definition	Type	Scale	Domain
Absenteeism	Refers to the total number of days absent from work due to illness	Quantitative	Numeric	In days
Absenteeism for COVID-19	Refers to the number of days absent from work due to COVID-19	Quantitative	Numeric	In days

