When you have a small sample and the numerical variable is not known to have a normal distribution (or cannot be verified satisfactorily), or when there is no homogeneity of variances, Student's t-test is not appropriate. In this situation, the nonparametric Mann-Whitney test (Wilcoxon rank-sum test, U-test) can be used. Unlike the t-test, which tests for equality of means, the Mann-Whitney test tests for equality of medians. The U values calculated by the test assess the degree of intermingling of the data of the two groups after sorting. The greater separation of the data together indicates that the samples are distinct, rejecting the hypothesis of equality of the medians. Total days of absenteeism will be analyzed using a Bayesian negative binomial regression with a fixed effect for BCG, hospital, professional category, age, enrolment week and number of average workdays per week. The excess absence of the event of interest can lead to data overdispersion (a phenomenon that occurs when the variance of the response variable is greater than the value of the mean). To check the overdispersion of the data we will use the deviance, which is also a statistic used to check the goodness of fit of the model.

The Kaplan-Meier method consists of dividing the follow-up time into intervals, whose limits correspond to the follow-up time when events occurred. The measure of association used in survival analysis to

compare groups is the Hazard Ratio (HR), with similar meaning to Relative Risk; HR is the probability that some participant who did not have the outcome event by a certain time, will have it at that time. HR therefore compares the instantaneous incidence with which events occur in the different groups (BCG and Placebo).

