Headache		% (n/N)	% (n/N)	
Muscle pain		% (n/N)	% (n/N)	
Sore throat	Categorical	% (n/N)	% (n/N)	
Diarrhea		% (n/N)	% (n/N)	
Loss of smell / taste		% (n/N)	% (n/N)	
Other		% (n/N)	% (n/N)	
Health problem in the past 2 weeks				χ^2 test or Fisher's exact test (P-value)
No		% (n/N)	% (n/N)	
Yes	Categorical	% (n/N)	% (n/N)	
Absent from work for the past 2 weeks due to illness				χ^2 test or Fisher's exact test (P-value)
No	Categorical	% (n/N)	% (n/N)	
Yes		% (n/N)	% (n/N)	
Days absent from work for the past 2 weeks	Quantitative	$\bar{X} \pm SD$ or Md (IQR)	$\bar{X} \pm SD$ or Md (IQR)	Student's t-test or Mann-Whitney test
Absent from work in the last 2 weeks due to a quarantine				χ^2 test or Fisher's exact test (P-value)
No	Categorical	% (n/N)	% (n/N)	
Yes		% (n/N)	% (n/N)	
Days absent from work in the last 2 weeks due to a quarantine	Quantitative	$\bar{X} \pm SD$ or Md (IQR)	$\bar{X} \pm SD$ or Md (IQR)	Student's t-test or Mann-Whitney test
Absent from work in the last 2 weeks due to illness				χ^2 test or Fisher's exact test (P-value)
No	Categorical	% (n/N)	% (n/N)	
Yes		% (n/N)	% (n/N)	
Days absent from work in the last 2 weeks due to illness	Quantitative	$\bar{X} \pm SD$ or Md (IQR)	$\bar{X} \pm SD$ or Md (IQR)	Student's t-test or Mann-Whitney test
Absent from work in the last 2 weeks due to COVID-19				χ^2 test or Fisher's exact test (P-value)
No	Categorical	% (n/N)	% (n/N)	
Yes		% (n/N)	% (n/N)	
Days absent from work in the last 2 weeks due to COVID-19	Quantitative	$\bar{X} \pm SD$ or Md (IQR)	$\bar{X} \pm SD$ or Md (IQR)	Student's t-test or Mann-Whitney test
Hospitalisation in the last 2 weeks due to illness				χ^2 test or Fisher's exact test (P-value)
No		% (n/N)	% (n/N)	
Yes	Categorical	% (n/N)	% (n/N)	
Nights hospitalisation in the last 2 weeks due to illness	Quantitative	$\bar{X} \pm SD$ or Md (IQR)	$\bar{X} \pm SD$ or Md (IQR)	Student's t-test or Mann-Whitney test
Hospitalisation due to COVID-19				χ^2 test or Fisher's exact test (P-value)
No	Categorical	% (n/N)	% (n/N)	
Yes		% (n/N)	% (n/N)	
Nights hospitalisation due to COVID-19	Quantitative	$\bar{X} \pm SD$ or Md (IQR)	$\bar{X} \pm SD$ or Md (IQR)	Student's t-test or Mann-Whitney test
Hospitalisation due other causes				χ^2 test or Fisher's exact test (P-value)
No	Categorical	% (n/N)	% (n/N)	
Yes		% (n/N)	% (n/N)	

Person living in the household diagnosed with COVID-19 in the last 2 weeks				
No		% (n/N)	% (n/N)	χ^2 test or Fisher's exact test (P-value)
Yes	Categorical	% (n/N)	% (n/N)	

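### SAP 6.2 names both LOCF and multiple imputation without saying which governs missing absenteeism; LOCF does not suit a 182-day total, and the primary model has no term for time observed

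*SAP*

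**What the plan says.** **Missing data.** SAP 6.2 states "We will use Last Observation Carried Forward (LOCF" and describes this single imputation in these words: "imputes the last measured outcome value for participants who either drop out of a clinical trial or for whom the final outcome measurement is missing". The next paragraph states "We will perform imputation of missing entries from incomplete data sets m times" and, after a step that turns missing categories into their own level, "After this procedure we will use multiple imputation". Neither multiple-imputation sentence is limited to covariates, and 6.2 never mentions absenteeism. The SAP's Statistical analysis section and the Protocol's Data analysis section both say "Missing data on background variables will be dealt with by multiple imputation"; neither covers a missing outcome.

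**Endpoint.** SAP Table 1 defines absenteeism thus: "Refers to the total number of days absent from work due to illness". Follow-up is 182 days with a telephone interview every second week. The item recorded (SAP Table 3) is "Days absent from work in the last 2 weeks due to illness".

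**Model.** SAP 6.4 states "Total days of absenteeism will be analyzed using a Bayesian negative binomial regression with a fixed effect for BCG, hospital, professional category, age, enrolment week", plus average workdays per week. The SAP's Statistical analysis section and the Protocol's Data analysis section give the same list. None of the three has an offset or other term for time observed. The Protocol abstract lists observation week where the others have age and enrolment week.

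**Back-up data.** The Protocol's Follow-up section sends staff to hospital registries after at least 18 days without an answer. SAP section 4 makes the workplace registry an optional supplement, at sites that have one.

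**Ceiling.** Above 10% missing, SAP 6.2 rules out imputation and leaves retention of the subject or the variable to the steering committee.

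**The concern.** An analyst could not tell from 6.2 what to do with a participant who stops answering. The most natural inference is LOCF for the outcome and multiple imputation for covariates. It is not written down, and it would put LOCF on the primary total.

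LOCF is meant for a state measured repeatedly, where the last value is a candidate for the final one. Here the final value is a sum, so it is unclear what is carried forward:

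- *Repeat*: the last fortnight's count is entered for every remaining fortnight.
- *Freeze*: the running total becomes the final total, which assumes no illness after dropout. With no exposure term in the model, partial follow-up then counts as full follow-up.

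Take a participant whose only absence is 3 days in fortnight 4 and who is then lost. Of the 13 fortnights 9 remain, so *repeat* gives 3 + 9 × 3 = 30 days and *freeze* gives 3. What was observed is 3 days in 56.

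Two neighbouring gaps make this worse. First, 6.2 does not say that registry data come first, and the available text does not say that the registries record the cause of absence. The endpoint needs the cause, because it excludes planned leave, family assistance and quarantine. Second, above 10% missing there is no alternative rule for the primary outcome. If the retention clause were used to drop people, it would conflict with the intention-to-treat statement.

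**Working it through.** **1. The plan's own figure.** Inputs: means 5 and 4 days, SD 5, two-sided 0.05, 80% power, 5% loss (Sample size sections; two-sided from SAP 6.1). n per arm = 2 × (1.960 + 0.842)² × 5² / 1² ≈ 393, so 786 in total and 786/0.95 ≈ 828 randomised. The stated 1050 is larger: power is 90.0% at 525 per arm and 88.5% at 499. That surplus is why power stays above 80% below.

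**2. Bias under freeze, closed form.** Let d₁ and d₀ be loss in BCG and placebo, and f the mean share of follow-up observed in those lost. If loss is unrelated to illness, the RR is multiplied by [1 − d₁(1 − f)] / [1 − d₀(1 − f)]. With f = 0.5 (dropout spread evenly over follow-up, assumed):

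- 5% v 5%: 0.975/0.975 = 1.000; the placebo mean falls from 5 to 5 × 0.975 = 4.88
- 7% v 5%: 0.965/0.975 = 0.990
- 10% v 5%: 0.950/0.975 = 0.974 (0.961 to 0.987 for f from 0.25 to 0.75)
- 15% v 5%: 0.925/0.975 = 0.949 (0.922 to 0.975)

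Simulation gives the same values to within rounding.

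**3. Simulation.** The documents give only mean 5 and SD 5, so the fortnightly pattern is assumed: gamma frailty, Poisson spells, geometric spell lengths with mean 1.5 to 3 days, at most 10 days per fortnight, 13 fortnights, calibrated to mean 5 and SD 5. Loss is random and balanced, with the last observed fortnight uniform on 1 to 12. Power uses 2,000 trials of 525 per arm and a maximum-likelihood negative binomial model without covariates, at two-sided 0.05. Monte Carlo error is about √(0.9 × 0.1/2000) = 0.7 points.

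Power (%) for RR 0.80, and the share of trials in which repeat and freeze disagree on p<0.05:

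| Loss | Mean spell | Repeat | Freeze | Offset | Disagree |
|---|---|---|---|---|---|
| 2.5% | 1.5 d | 92.7 | 92.7 | 93.0 | 2.6% |
| 2.5% | 3 d | 86.0 | 86.6 | 86.9 | 6.0% |
| 5% | 1.5 d | 92.2 | 93.2 | 93.8 | 4.0% |
| 5% | 3 d | 85.2 | 87.7 | 87.8 | 7.8% |
| 10% | 1.5 d | 89.6 | 91.3 | 92.1 | 5.7% |
| 10% | 3 d | 81.2 | 86.2 | 87.2 | 11.1% |

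The 2.5% rows stand for registries recovering half the planned loss, which is an assumption. At RR 1 and 5% loss the readings disagree in about 3% of trials.

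**4. Precision.** At 5% loss, the SE of log RR (repeat/freeze/offset) is 0.0653/0.0631/0.0626 for 1.5-day spells and 0.0709/0.0664/0.0663 for 3-day spells. Variance of repeat relative to offset is (0.0653/0.0626)² = 1.09 and (0.0709/0.0663)² = 1.14. That is like losing 1050 × (1 − 1/1.09) ≈ 87 and 1050 × (1 − 1/1.14) ≈ 129 participants. Freeze is 0 to 2% above offset. The outcome variance itself rises under repeat by 9 to 20% at 5% loss and by 19 to 44% at 10%.

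**5. Illness-linked loss (assumed; about 5% loss, true RR 1).** If dropout is twice as likely after a sick fortnight in placebo only, repeat gives RR 0.98 to 0.985. At five times as likely it gives 0.94 to 0.965. If the link holds in both arms, repeat is unbiased. The offset stays within 0.01 of the truth here and in every scenario of step 2.

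**The case against.** The strongest reply is that this is a clarification and not a threat to the result.

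- *The text can be read coherently.* LOCF is tied to an outcome value, and multiple imputation is elsewhere tied to background variables. This stands as a likely intention, but it is unwritten, 6.2's own wording is broader, and it leaves LOCF on the total.
- *Freeze does almost as well as the offset at planned loss.* It does, and the endpoint is a total, so freeze may be what was meant. Under illness-linked loss in placebo only, freeze gave 0.999 to 1.006 of the truth, no worse than the offset's 0.991 to 0.997. Its bias appears when loss rates differ. No document suggests that they will, and blinding makes it less likely.
- *Disagreement needs a benchmark.* Two analyses that are both unbiased, offset and complete-case, also disagree in about 2 to 5% of simulated trials. Much of the 4 to 8% is therefore ordinary crossing of p = 0.05. It supports fixing one rule in advance more than it counts against LOCF itself.
- *The comparison is partial.* Multiple imputation of the outcome was not simulated, and the planned model is Bayesian with covariates and monthly looks.
- *Other text helps.* SAP 6.2 requires the extent and reasons of missingness to be reported, 6.3 plans participant flow by arm, and the Protocol's ethics section has attendance registers checked every second week where available. These would help to reveal differential loss, but they do not say how to analyse it. Parts of both documents were unavailable, so silence on cause coding in the registries is a question for the sites.

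**Conclusion.** The concern holds and should be fixed, at moderate weight. The SAP does not state one rule for missing absenteeism, LOCF is a poor match for a cumulative count, and the model cannot allow for shortened follow-up.

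At 5% balanced loss the RR is unbiased and power exceeds 80% under both readings of LOCF. The cost at that loss is 1.6 to 2.6 power points if fortnights are repeated and almost nothing if the total is frozen. What remains is an open choice that can change the primary verdict on the same data, and exposure to bias of about 1 to 5% in the RR if loss differs by 2 to 10 percentage points between arms (freeze), or of up to about 6% if illness drives loss in one arm only (repeat).

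The power and precision figures depend on the assumed spell pattern, and the bias figures on assumed contrasts between arms. The textual gap depends on neither.

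**What to change.** Fix one rule before unblinding:

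1. Delete LOCF for absenteeism. Fit the negative binomial model to observed illness days with an offset of log(days observed).
2. Keep every randomised participant with any observed time, and report by arm those with none.
3. Use registry data first, but count that time as observed only where the registry identifies illness as the cause of absence; otherwise the fortnight is unobserved. Decide this per registry and not per day, because keeping days marked present while dropping unexplained absences would lower the rate.
4. State that the multiple-imputation paragraph in 6.2 covers background variables.
5. Add fortnight-level multiple imputation of the outcome as a sensitivity analysis, including one scenario of illness-related dropout.
6. Reconcile observation week in the Protocol abstract with the other three model lists. If it means weekly records, time observed would enter differently.
7. Remove the subject from the retention clause, and say that the offset rule also applies to the primary outcome above 10% missing.
8. State the limit: the offset assumes that unobserved time resembles observed time.

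The cost is SAP wording, one variable derived from interview dates and registry retrieval already planned, a check of which site registries record cause, and some programming for the sensitivity analysis. Participants with no observed time contribute nothing to the primary model.
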